## **4.0 Treatments**

**4.1 Prescribed Study Treatments.** Patients in whom dabigatran is initiated within 14 days of TIA/stroke symptom onset will be included in the registry. The timing of initiation of therapy within that 14 day window will be determined by the treating physician. The factors related to physician choice of initiation time (relative to symptom onset) will be recorded (**appendix 5**).

**4.1.1 Identity of test products and comparators.** NA.

**4.1.2 Treatment Group Assignment.** NA.

**4.1.3 Selection of Dose.** Patients will be treated either at a dose of 110 mg BID or 150 mg BID. The dose will be determined by treating physician. The physician rationale for the dose selected will be recorded in all cases (**appendix 6**).

## **5. Variables and Assessment.**

**5.1.1 Effectiveness.** This is a registry of the safety of early anticoagulation (see 5.2). A measure of the effect of early anticoagulation will be assessed; the rate of new ischemic stroke/TIA occurrence within the 30-day study period will be recorded. It is recognized that the event rate will be low and the study is neither designed, nor powered to demonstrate a decrease in early ischemic stroke rates.

**5.1.2 Primary Outcome (Safety).** The primary study outcome measure is the symptomatic hemorrhagic transformation rate (PH2 associated with clinical deterioration, defined as worsening of NIHSS score of 4 or more points, within 30 days of initiating dabigatran therapy).

### **5.1.2 Secondary Outcomes.**

The rate of any objective hemorrhagic transformation on the day 7 post-dabigatran initiation non-contrast CT scan.

The rate of secondary hemorrhagic transformation in patients taking warfarin prior to the stroke/TIA.

The rate of hemorrhagic transformation in patients started on dabigatran within 7 days of stroke/TIA versus those started >7 days after symptom onset. Recurrent TIA/Ischemic Stroke within 30 days of dabigatran initiation.

Systemic hemorrhagic complication rate within 30 days of dabigatran initiation.

The rate of hemorrhagic transformation in patients started on dabigatran within 7 days of stroke/TIA versus those started >7 days after symptom onset.

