**Statistical Analyses:**

The primary outcome will be occurrence of PH2 at 30 days. Secondary outcomes will be ischemic stroke, any intracerebral hemorrhage, MI and death. In addition we will compare the rate of hemorrhagic transformation in patients started on dabigatran within 7 days of stroke/TIA versus those started  $>7$  days after symptom onset.

Descriptive statistics will be used to describe all outcomes (see protocol section 7.1).

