#### *Timing of Anticoagulation after Cardioembolic TIA/Stroke:*

It is clearly established that patients with atrial fibrillation who have suffered a stroke/TIA are at high risk for recurrence and require long-term anticoagulation. What is unknown is the optimal timing of anticoagulation after an ischemic stroke has occurred. Following cardioembolic stroke, atrial fibrillation patients are at risk for early recurrent thrombo-embolism. Estimates of the rate of recurrent stroke in this setting vary widely. Previous studies have indicated new ischemic strokes occur at rates anywhere from 3% to 20% within two weeks of the index event. This is the primary rationale for early anticoagulation after cardioembolic stroke. There is some evidence that early anticoagulation is associated with improved outcomes after ischemic stroke. Indeed, it has been shown that early heparin use does reduce recurrent ischemic stroke risk by 2.1%, but this is offset by a 1.7% increase in the rate of HT. Studies of low molecular weight and unfractionated heparin use in acute stroke have generally indicated these agents are associated with moderately increased risk of HT. There are currently no data indicating the frequency of HT associated with early warfarin treatment, without heparin bridging.

Based on the above evidence, current best practice guidelines recommend against urgent anticoagulation in patients with moderate to severe ischemic stroke, however, due to the elevated risk of hemorrhagic transformation (HT) immediately after stroke. A specific time point at which to begin anticoagulation is not recommended in guideline statements. This clinical equipoise has resulted in significant variation in practice patterns. Currently, most CSC physicians base the timing of anticoagulation on clinical severity and infarct size, as seen on CT scan. Most physicians will defer anticoagulation anywhere from 5 to 14 days after ischemic stroke when infarct volume is extensive. In patients with small infarct volumes, assessed with CT or MRI, however, anticoagulation is often begun within 24-72 hours of stroke onset, and in some cases immediately after clinical assessment and CT scan.

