## **7. Statistical Methods and Sample Size**

**7.1 Statistical Analysis and Sample Size Considerations:** The registry will include 500 patients. This sample size is considered adequate to ensure inclusion of a significant number of patients treated at a range of time points within the post-stroke period. The primary analysis will be done on an Intention

To Treat basis. We will also complete a sensitivity analysis on individuals who discontinued dabigatran treatment and/or switched to other antithrombotic agents. Based on the inclusion/exclusion criteria, there will not be any individuals taking dabigatran concomitantly with other antithrombotic drugs.

The primary and secondary outcomes will be defined with descriptive statistics. The rate of PH2 (and all other forms of hemorrhagic transformation) will be defined as a ratio (%) of the total number of patients enrolled in the study (ITT analysis).

The primary stratification variable is warfarin use prior to the TIA/minor stroke. The secondary strata are 1. Dabigatran dose (150 mg BID versus 110 mg BID) and 2. Time to initiation of therapy (0-2 days, 3-7 days and > 7 days). All results including baseline patient characteristics will be stratified by use of warfarin prior to the event and by the dabigatran dose after the event as described in **appendices 2-4**.

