**Limitations.** There are recognized limitations to this study. The eligibility criteria are consistent with a low risk population, and the results of this study will not be generalizable to other, higher risk stroke/TIA populations. Even in the population of TIA and minor stroke patients, the time between symptom onset and treatment initiation may vary with the severity of the clinical presentation. Although it is not our intention, clinicians may be more likely to initiate therapy earlier in patients with complete resolution of all neurological deficits. Only dabigatran treated patients will be included in this registry. Unintended selection bias may also arise from survival bias over the time from incident stroke/TIA to time of dabigatran treatment and start of follow-up. Finally this is a small (500) single arm study with a relatively short (30 day) follow-up period. This short time period will permit assessment of the most important safety variable (hemorrhagic transformation rates). It will also minimize loss to follow-up. Although functional outcome is generally assessed at 90 days, this pilot study is too small to adequately assess that endpoint.

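### The comparison of haemorrhagic transformation by start time (within 7 days versus later) is not split by TIA and minor stroke, although index event may drive both start time and outcome

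*Combined protocol and SAP*

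**What the plan says.** The Synopsis, under Statistical Analyses, commits to the contrast: "In addition we will compare the rate of hemorrhagic transformation in patients started on dabigatran within 7 days of stroke/TIA", against those who start later. Section 5.1.2 (Secondary Outcomes) lists it twice: "The rate of hemorrhagic transformation in patients started on dabigatran within 7 days of stroke/TIA versus those started >7 days after symptom onset". Neither place says which grade of haemorrhagic transformation (HT) is meant.

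Section 4.1 bounds the late group at day 14: "Patients in whom dabigatran is initiated within 14 days of TIA/stroke symptom onset will be included in the registry". The treating physician chooses the start time within that window.

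On analysis, section 7.1 says "The primary and secondary outcomes will be defined with descriptive statistics". Results are stratified by prior warfarin use and by dose, and time to initiation is a further stratum. Index event, NIHSS and infarct size are not strata.

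On what drives start time, section 1.1 says "most CSC physicians base the timing of anticoagulation on clinical severity and infarct size, as seen on CT scan". The Limitations paragraph of section 7.1 adds, for the TIA and minor-stroke population itself, that "the time between symptom onset and treatment initiation may vary with the severity of the clinical presentation" and that "clinicians may be more likely to initiate therapy earlier in patients with complete resolution of all neurological deficits". It also warns that "Unintended selection bias may also arise from survival bias over the time from incident stroke/TIA to time of dabigatran treatment".

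Appendix 3 tabulates index event by start time but has no outcome rows. Appendix 4 holds the outcomes, by prior treatment and dose, without index event.

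**The concern.** A factor confounds this contrast if it is tied to both start time and HT. On the plan's own account, index event may be both. The Limitations paragraph links full resolution of deficits to an earlier start. In section 5.2.3, HT1, HT2, PH1 and PH2 are each defined relative to an infarct, so a TIA patient with no infarct cannot receive any of them; only remote haemorrhage remains.

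If early starters include more TIA patients, their HT rate can be lower for that reason alone. Section 1.1 ranks the timing of initiation as the most important clinical problem, so readers will look for this secondary result. The risk is over-reading it. The primary outcome is not affected.

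**Working it through.** **1. Where index event appears.**

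| Place | Start time | Index event | HT outcome |
|---|---|---|---|
| Synopsis and section 5.1.2, planned contrast | yes | no | yes |
| Section 7.1 strata (prior warfarin, dose, time to initiation) | yes | no | yes |
| Appendix 3 | yes | yes | no |
| Appendix 4 | bands labelled as days after drug initiation | no | yes |

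No row has all three.

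**2. The plan's own figure.** Section 2.3 takes 1.7% with heparin and a one-third ratio: 1.7% × 1/3 = 0.57%, stated as 0.6%. Then 500 × 0.006 = 3.0 symptomatic events in all. If 20% start late (assumed, n = 100), 0.6 events are expected there and the chance of none is 0.994^100 = 0.55. If 50% start late (n = 250), 1.5 are expected and the chance is 0.994^250 = 0.22. Symptomatic HT cannot support a split or a model.

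**3. Illustration for any HT.** The documents give no HT risk by severity and no early or late shares, so every input here is assumed. There is no true timing effect, and TIA patients are half of the sample on average. The ranges are:
- HT 2 to 8 times as frequent after stroke as after TIA;
- TIA share 10 to 30 points higher in early starters;
- within stroke, the more severe half with 2 to 4 times the risk, and 10 to 30 points less common in early starters;
- late share 20 to 50%.

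Middle case (factors 4 and 3, both differences 20 points, 35% late). Set TIA risk at 1 unit and mean stroke risk at 4, so less and more severe strokes carry 2 and 6 units.
- Early stroke risk: 0.6×2 + 0.4×6 = 3.6. Late: 0.4×2 + 0.6×6 = 4.4.
- Without an index-event split: (0.6×1 + 0.4×3.6) / (0.4×1 + 0.6×4.4) = 2.04/3.04 = 0.67.
- Mantel-Haenszel over index event, with 195 TIA and 130 stroke early, 70 and 105 late: (195×70/265 + 130×3.6×105/235) / (195×70/265 + 105×4.4×130/235) = 260.6/307.1 = 0.85.

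Over the full ranges the unsplit ratio is 0.45 to 0.90 and the stratified ratio 0.72 to 0.96. Stratifying brings it closer to 1 but not to 1, because severity still differs within stroke.

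**4. Survival bias.** Section 3.3 follows only treated patients. If a fraction f of would-be late HT cases never enters, the early:late ratio is multiplied by 1/(1 − f). With f = 0.1 to 0.3 (assumed):

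| Case | Unsplit / stratified, f = 0 | f = 0.1 | f = 0.3 |
|---|---|---|---|
| Mild (low end of each range) | 0.895 / 0.956 | 0.99 / 1.06 | 1.28 / 1.37 |
| Middle | 0.671 / 0.849 | 0.75 / 0.94 | 0.96 / 1.21 |
| Strong (high end of each range) | 0.454 / 0.720 | 0.50 / 0.80 | 0.65 / 1.03 |

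The combined ranges are 0.50 to 1.28 unsplit and 0.80 to 1.37 stratified, and both include 1. At f = 0.3 the stratified ratio lies further from 1 than the unsplit one in the mild and middle cases, and in about 82% of combinations over the full ranges.

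**5. Precision.** Assume 4% any HT (20 events), a 20-point difference in TIA share and no severity difference within stroke. The 95% interval then multiplies and divides the ratio by 2.37 to 2.80 unsplit and 2.38 to 2.83 stratified. At 2% the factors are 3.42 to 4.37 and 3.47 to 4.44; at 8%, 1.81 to 2.04 and 1.81 to 2.05. Of the 20 events, about 2 to 8 fall in TIA patients, and only 0.4 to 2.7 of those in late starters.

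**The case against.** Much of the problem is already disclosed or softened. The Limitations paragraph names severity-driven timing, its likely direction and survival bias. Appendix 3 will show any imbalance in index event, and Appendix 5 records the physician's reasons for timing, including NIHSS and infarct size. Section 7.2 calls the study hypothesis generating, and the planned analysis is descriptive. All of that stands and lowers the priority. It does not close the gap, because disclosure leaves the rates as they are and Appendix 3 cannot show what an imbalance does to HT.

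Section 1.1 describes stroke practice at large. The registry takes only TIA and NIHSS of 3 or less, lists extensive infarction as a contraindication and expects no acute ischaemic change on baseline scans, so the severity range is narrower. That also stands. The argument rests on the Limitations paragraph, which speaks of this population and says only that timing may vary. Nor is TIA a risk-free stratum: section 1.1 treats TIA and minor stroke as a continuum.

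The correction may be lost in noise. In the middle case it moves the ratio by 0.849/0.671 = 1.27, against interval factors of 2.4 to 2.8 at 4% HT. This is a good reason not to make a pooled ratio the main product. It does not argue against showing the counts.

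A reader might also infer that the contrast is wholly crude. It is not, since section 7.1 stratifies all results by prior warfarin use and dose. The gap concerns index event and severity.

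**Conclusion.** The point holds as an inexpensive improvement of low to moderate priority to one secondary comparison. As written, the contrast can mix start time with TIA/stroke case mix, and data already planned for collection would show how far. The only size that rests on the documents is the 3.0 expected symptomatic events. All HT ratios above depend on assumed shares and risks and show possible size only.

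Three stronger readings are tempting, and the documents support none of them.
- That early start will look safer than it is. Severity-driven timing alone would push that way, but survival bias may push back and neither size is given.
- That stratifying by index event corrects the estimate. It leaves severity and infarct size within minor stroke, and removing one of two opposing biases can leave the net result worse.
- That the analysis is missing because the Appendix 4 rows count from drug initiation. The Synopsis and sections 5.1.2 and 7.1 commit to it. Appendix 4 uses the same bands as the section 7.1 strata, and the documents do not settle whether its label is a slip or intended.

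**What to change.** 1. State which grade of HT the comparison uses; any HT is the workable choice.
2. Beside the overall rates, report events over patients by start-time group separately for TIA and minor stroke. Give exact 95% intervals for minor stroke and counts only for the sparse TIA cells. Tabulate baseline NIHSS by start-time group within minor stroke.
3. Leave symptomatic HT as counts. An index-event-stratified Mantel-Haenszel ratio with its interval may be added, labelled exploratory.
4. State beside the table that the result is a non-causal association, that confounding by severity and infarct size remains within minor stroke, and that, because survival bias may oppose severity confounding, stratifying does not guarantee a less biased net estimate.
5. Minor: reconcile the Appendix 4 row labels with the time-to-initiation strata in section 7.1, so that one shell shows outcomes by onset-to-start time. If time from first dose to event is also wanted, list it separately.

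The cost is analysis and table wording only. Index event (Appendix 3), onset-to-start time (section 6.2.2) and baseline NIHSS (section 6.1) are already collected. The downsides are very small late-TIA cells and one more table that could be over-read, which is why the statement in item 4 belongs next to it.

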## Synopsis

**Study Title:** Canadian Pradaxa Acute Stroke Safety Study (CPASS)

**Protocol Number:** CSC2012-01

**Development Phase:** Phase IV Registry

**Indication:** Minor Stroke (NIHSS Score  $\leq 3$ ) and Transient Ischemic Attack Patients with a known history of or demonstrated atrial fibrillation (paroxysmal or persistent), who can be treated with dabigatran following stroke.

**Study Drugs:  
(Including test,  
comparator, dosage  
form, dosing regimen  
and route)** Dabigatran Etxilate  
Dose: 150 mg PO BID OR 110 mg PO BID (dose determined by patient age and renal function)  
Route: PO  
  
Comparator : None (open label, single arm trial)

**No. Subjects:** 500

**No. Centres:** 15 centres within Canada

**Study Duration:** 2 years. Patients will participate in the trial for 1 month.

**Objectives of the Study:** The primary aim of the CPASS registry is to demonstrate the safety of early anticoagulation with dabigatran following cardioembolic stroke. Safety will be established by demonstrating low rates of hemorrhage in this setting.

**Study Endpoints:  
(Primary and  
Secondary)** *Primary Outcome*  
Symptomatic Hemorrhagic Transformation Rate (PH2) associated with clinical deterioration, defined as worsening of NIHSS score of 4 or more points within 30 days of initiating dabigatran therapy.

*Secondary Outcomes*  
Any parenchymal haemorrhage (PH1 or PH2) on follow-up CT scan at 7 $\pm$ 2 days post-enrolment

Symptomatic hemorrhagic transformation rate (defined as above) in patients treated with warfarin prior to the index stroke/TIA.

Recurrent TIA/Ischemic Stroke within 30 days of enrolment  
 Systemic hemorrhagic complication rate within 30 days of enrolment

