- Concomitant treatment of dabigatran etexilate with any other anticoagulant, including unfractionated heparin (UFH), except at doses used to maintain a patent central venous or arterial catheter, low molecular heparins (LMWH), such as enoxaparin and dalteparin, heparin derivatives, such as fondaparinux, anti-thrombin agents, such as bivalirudin, and oral anticoagulants, such as warfarin, rivaroxaban, apixaban, except under circumstances of switching therapy to or from dabigatran
- Presence of prosthetic heart valve(s) requiring anticoagulation due to valvular status itself

Patients with a history of symptomatic ischemic stroke prior to the index event will not be eligible. All patients taking dabigatran or any other novel oral anticoagulant (including all Factor Xa antagonists) prior to the stroke will be ineligible. Individuals on warfarin at the time of the incident event are eligible, provided the INR is  $\leq 1.5$  prior to initiation of dabigatran.

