## **6. Investigational Plan**

**6.1 Visit Schedule / Clinical Data Collection.** No additional procedures or assessments will be mandated for study participants. Standard clinical assessments and data will be collected. This will include baseline National Institutes of Health Stroke Scale NIHSS, Glasgow Coma Scale (GCS) and vital signs, which will be recorded in a case report form. Stroke risk factors, past medical history and medications, baseline complete blood count, coagulation profile and renal function tests will also be recorded. CHADS2 and CHADSVaSC scores will also be recorded. Clinical endpoints will be ischemic stroke or intracranial hemorrhage within 30 days of anticoagulant initiation. All cerebral ischemic and intracranial hemorrhagic endpoints will be centrally adjudicated from anonymized clinical records, with the intracranial hemorrhages classified as described above. A data collection form will be filled out for each subject at 30 days post-enrolment indicating clinical status and occurrence of outcome events.

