### **6.2 Details of Study Procedures**

**6.2.1 Screening and run-in procedures.** NA.

**6.2.2 Treatment Period.** Patients will be treated long-term with dabigatran if deemed appropriate by the attending physician and the patient is in agreement. The study outcome event period is 30 days from drug initiation. The SAE reporting period is an additional 7 days.

The time from symptom onset to dabigatran initiation will be recorded in the CRF. In all cases, dabigatran will be prescribed by a stroke neurologist participating in the registry. The location of the patient at the time of dabigatran initiation will be recorded (inpatient/outpatient/Emergency Department).

**6.2.3. End of Trial and follow-up.** The registry data collection period will be complete after 30 days.

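### The 30-day recurrence rate is counted from the first dose, so it cannot serve as a measure of the effect of early anticoagulation, and it should not be compared across start times

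*Combined protocol and SAP*

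**What the plan says.** Section 5.1.1 says of the recurrence rate: "A measure of the effect of early anticoagulation will be assessed". It adds that the event rate will be low and that the study is neither designed nor powered to show a decrease.

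In the body of the protocol the clock starts at the first dose. Section 5.1.2 (Secondary Outcomes) has "Recurrent TIA/Ischemic Stroke within 30 days of dabigatran initiation". Section 6.1 has "Clinical endpoints will be ischemic stroke or intracranial hemorrhage within 30 days of anticoagulant initiation". Section 6.2.2 has "The study outcome event period is 30 days from drug initiation". The synopsis differs: "Recurrent TIA/Ischemic Stroke within 30 days of enrolment".

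On the delay, section 4.1 says "Patients in whom dabigatran is initiated within 14 days of TIA/stroke symptom onset will be included in the registry", with the day left to the treating physician. On the risk to be prevented, section 1.1 says "new ischemic strokes occur at rates anywhere from 3% to 20% within two weeks of the index event" and gives this as the main reason for anticoagulating early.

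Section 3.3 keeps a log of all consented patients but follows only those treated. Section 7.1 names time to initiation (0-2, 3-7 and more than 7 days) as a secondary stratum. The Limitations paragraph mentions survival bias between the event and the start of follow-up, but no analysis deals with it.

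**The concern.** The permitted delay and the risk period are the same two weeks. Starting early can help only by protecting patients on days when a late starter is still untreated, and the outcome leaves those days out. A patient who starts on day 14 has the whole two-week risk period outside the window.

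The start bands are also observed over different stretches of time since onset. A day-1 starter is watched from day 1 to day 31, a day-14 starter from day 14 to day 44. If the hazard declines with time since onset, the later window is the safer one whatever the drug does.

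Early recurrence may also keep a patient out of the registry. A recurrent stroke may exceed the NIHSS limit of 3. If the recurrence is taken as the index event, a first minor stroke becomes a prior stroke, and "Patients with a history of symptomatic ischemic stroke prior to the index event will not be eligible". Late starters are then selected for having stayed free of recurrence.

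The timing of initiation is the problem that section 1.1 calls most important. A table of recurrence by start band could make delay look harmless or protective when it is neither.

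**Working it through.** The documents give no calculation for recurrence, so there is no figure of the plan's own to reproduce. The check asks how far the first-dose clock alone can separate early from late starters.

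**Inputs from the protocol.** The 14-day risk R is 3% or 20% (section 1.1). The start day s lies between 0 and 14 (section 4.1). The window is 30 days from the first dose (sections 5.1.2, 6.1 and 6.2.2).

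**Assumptions not in the protocol.** The hazard is constant to day 14, then r times that value. In step 1 the drug has no effect.

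**Step 1: first-dose clock, no drug effect.**
- Daily hazard: h = -ln(1 - R)/14. For R = 3%, h = 0.002176.
- Days observed in the early period: 14 - s. Later days observed: 30 - (14 - s) = 16 + s.
- Risk = 1 - exp(-h × [(14 - s) + r(16 + s)]).
- Early and later days are 13 and 17 for s = 1, 7 and 23 for s = 7, and 3 and 27 for s = 11.
- Example, r = 0.2: for s = 1, 13 + 0.2 × 17 = 16.4 and the risk is 3.5%. For s = 11, 3 + 0.2 × 27 = 8.4 and the risk is 1.8%. The ratio is 1.9.

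Results for R = 3%:

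| r | day 1 | day 7 | day 11 | ratio, day 1 to 11 | ratio, day 1 to 7 |
|---|---|---|---|---|---|
| 0 | 2.8% | 1.5% | 0.65% | 4.3 | 1.85 |
| 0.2 | 3.5% | 2.5% | 1.8% | 1.9 | 1.4 |
| 0.5 | 4.6% | 3.9% | 3.5% | 1.3 | 1.16 |
| 0.8 | 5.6% | 5.4% | 5.2% | 1.08 | 1.05 |
| 1 | 6.3% | 6.3% | 6.3% | 1.0 | 1.0 |

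For R = 20% the day-1 to day-11 ratios are 4.0, 1.8 and 1.25 at r = 0, 0.2 and 0.5.

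**Step 2: risk that falls before the first dose.** This is 1 - exp(-h × s). For starts on day 1, 7 and 14 it is 0.2%, 1.5% and 3.0% when R = 3%, and 1.6%, 10.6% and 20.0% when R = 20%. None of it is counted.

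**Step 3: the same question with a real drug effect.** Section 2.3 expects a reduction of at least 85%, so the hazard is multiplied by 0.15 after the first dose. Take r = 0.25 and R = 3%.
- First-dose clock: 1 - exp(-0.15 × h × [(14 - s) + 0.25(16 + s)]). The bracket is 17.25, 12.75 and 7.5 for starts on day 1, 7 and 14, which gives 0.56%, 0.42% and 0.24%.
- Onset clock to day 30, pre-dose events counted: 1 - exp(-h × [s + 0.15 × ((14 - s) + 0.25 × 16)]). The bracket is 3.55, 8.65 and 14.6, which gives 0.8%, 1.9% and 3.1%.
- For R = 20% the two sets are 4.0%, 3.0%, 1.8% and 5.5%, 12.9%, 20.8%.

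The order reverses. Where early treatment works well, the planned measure ranks the late starter as better off. If r = 1, the first-dose clock gives 0.97% for every start day (R = 3%), so no benefit of an early start is visible.

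**The case against.** The protocol limits its own claim. Section 5.1.1 disclaims design and power, section 7.2 calls the study hypothesis generating, section 7.1 keeps the outcomes descriptive, and the Limitations paragraph names survival bias. These caveats lower the stakes. They do not answer the point: lack of power concerns precision, and a larger sample would leave this bias in place.

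A reader might infer that the plan contains a biased early-versus-late comparison of recurrence. It sets out no such comparison. The explicit contrast at 7 days is for hemorrhagic transformation. Appendix 3 tabulates characteristics, not outcomes, by start band. The recurrence rows of Appendix 4 count days after initiation. The sentence in section 7.1 that covers all results stratifies by prior warfarin and by dose. The exposure comes from naming time to initiation as a stratum. Likewise, no section plans to set the registry rate against the 3% to 20% figure, although section 2.3 quotes that range beside the expected reduction.

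A reader might also infer that late starters must look better. That needs a hazard that falls with time since onset. The emphasis on early recurrence makes this plausible, but the documents do not establish it. Nor does heavier front-loading always widen the gap, because the day-1 starter also misses the earliest risk. With a 1-day half-life within the first 14 days, R = 3% and r = 0.5, the rates are 3.3% and 2.9%, a ratio of 1.15 against 1.3 under a constant hazard.

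Finally, day 1 against day 11 is a wide pair. Section 1.1 links delays of 5 to 14 days to extensive infarcts, and this registry takes minor stroke and TIA. The day-1 to day-7 column is the more moderate reading.

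**Conclusion.** The point holds in two parts. First, and without any modelling assumption, a rate that counts only events after the first dose cannot show what starting earlier prevents, so the description in section 5.1.1 is not supported. Second, and conditionally, reporting that rate by start band would favour late starters if the hazard falls after the first two weeks. In the 3% case the factor is 1.3 to 4.3 for day 1 against day 11 and 1.16 to 1.85 for day 1 against day 7, with the later hazard between 50% and 0 of the early one. There is no distortion if the hazard stays constant.

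The outcome is secondary, descriptive and unpowered. The point does not touch the primary hemorrhage outcome, for which counting from the first dose is appropriate. A change is worth making because it is cheap and timing is central to the registry. The documents do not support the stronger conclusion that a change of clock would let this registry measure the benefit of early treatment.

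**What to change.** 1. Keep the 30-day-from-dose rate as a descriptive rate after starting dabigatran, and reword section 5.1.1 so that it is not called an effect of early anticoagulation.
2. Reconcile the enrolment clock in the synopsis with the first-dose clock in sections 5.1.2, 6.1 and 6.2.2. Because the section 3.3 log includes consented patients who are never treated, consent can precede the first dose. An enrolment clock would still miss events before enrolment.
3. Add an analysis of recurrence by day since onset, with each patient entering at the first-dose day, and compare start bands only over the same days since onset. Days 14 to 30 are common to all: the latest entry is day 14 and the earliest end is day 0 + 30.
4. Record any stroke or TIA between index onset and first dose in the CRF and, for consented patients, in the section 3.3 log.
5. State that the 30-day-from-dose rate is not to be compared across start bands or with the 3% to 20% figure.
6. State the remaining limit. Patients who recur before consent are not seen, and those never treated are not followed. Items 3 and 4 remove the unequal windows and document known pre-dose events, but they do not make the benefit of an early start estimable.

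The cost is plan wording, one CRF item and one log item. Section 6.2.2 already records onset-to-dose time. Late starters contribute fewer comparable days, so the band comparison loses precision.
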